4.3. Exploratory Analysis of Safety Outcomes

The frequency with which various side effects, adverse event (AE) or serious adverse events (SAE) occur will be carefully tabulated and descriptively summarized.

Statistical comparisons of the randomized arms with respect to these events will use chi-square, Fisher exact or other appropriate two-sample methods depending on the nature of the event, interpreting such comparisons in the context of differences between the two randomized arms in the primary and major secondary outcomes and bringing to bear clinical judgment as to the relative seriousness of these side effects and various adverse events.

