8.2. Randomization and Patient Analgesic Protocols

After patients have provided informed written consent, they will be randomized to either

the weight-based analgesic protocol or a patient-specific analgesic protocol that will be developed by their hematologist/sickle cell team. A 1:1 treatment allocation will be used with site as the stratification variable. A computer-generated permuted block randomization schedule with stratification by clinical site will be prepared by the DCC senior statistician with block size randomly chosen that will not be revealed to investigators. This scheme provides chronological balance during enrollment with respect to the number of patients allocated to each treatment arm, and thus balances the treatment groups with respect to possible changes in the mix of patients over time. For the sites, the randomization will be available through the password protected and customized web-based electronic data capture (EDC) system. The EDC will be maintained by the DCC data management team. Treatment plans can be updated as needed by the hematologist.

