Repeat doses	TBD by SCD provider – Q 20-30 minutes as required to treat unrelieved pain. No maximum dose set.	Q 20-30 minutes for unrelieved pain. All additional doses, if required, may be provided at the same dose as the 1 st dose, or no more than a one time 25% increase above the original dose.
Intravenous hydration	Maintenance rate (unless dehydrated) when patients are unable to drink fluids adequately.	Maintenance rate (unless dehydrated) when patients are unable to drink fluids adequately.

Once the patient’s analgesic protocol has been developed (patient-specific or weight-based) by the hematologist/sickle cell team, the research team will be notified. The research team will ensure the analgesic protocol is uploaded to the electronic medical record (EMR) within one week of receipt. The analgesic protocol will be available in the EMR for future ED visits.

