13. STATISTICAL CONSIDERATIONS

13.6. Overview

Detailed description of the plan for statistical analysis of each endpoint will be detailed in a Statistical Analysis Plan (SAP) that will be prepared after the final study protocol is approved. The SAP will be prepared by the DCC senior statistician under [name] supervision.

Descriptive statistics will be used to summarize patient socio-demographic and clinical characteristics. The analyses of primary and secondary outcomes as well as the summary description of pain-related side effects and safety will be carried out by the DCC statistical service. Means, standard deviations, medians, 25th and 75th percentiles, minimum and maximum will be presented for continuous variables; the number and frequency of patients in each category will be presented for nominal variables. For all analyses, a two-sided p-value ≤ 0.05 will be considered statistically significant. Analyses will be performed using SAS version 9.4 or higher software (SAS Institute, Inc., Cary, NC).

Multiple Comparisons: With the pre-specified primary and secondary analyses, we

recognize that there is a multiplicity of analyses to be performed, which leads to an increased probability that at least one of the comparisons could be "significant" by chance. There are adjustments (e.g., based on the Bonferroni inequality) that can be used to preserve the overall type I error level. To attempt to adjust for the effects of the repeated significance testing that will occur as part of potential interim monitoring (discussed below), plus to adjust for the multiplicity of secondary outcomes, would require that very small significance levels be used for every comparison. Rather than taking this approach we will be conservative in the interpretation of secondary analyses, taking into account the degree of significance, and looking for consistency across outcomes. The actual p-value for each comparison will be reported to aid in the overall interpretation. In addition to the pre-specified primary outcome, we will use pre-specified secondary outcomes and pre-specified subgroups to help avoid over-interpretation and to help guard against and reduce the problems inherent with multiple testing.

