Power calculation for the secondary outcomes are performed for the target sample size of 230 at 0.05 level. We do not expect any missing data in the secondary outcomes, as seen in the R34 study. For the length of ED stay from arrival to discharge, we have 83% power to detect a 30-minute difference in length of ED stay between the two analgesic protocols, assuming SD of 78. In the R34 study restricting to the first ED visit, the mean (SD) length time from arrival to discharge was 278 minutes (SD=78). For the secondary outcome of (yes/no) hospital admission in the 1st ED visit, returned ED visit or hospital admission within 7 days of the 1st ED visit, we use 15% as clinical significant difference. We have 64%, 78% and 94% power to detect a 15% difference in hospitalization rates in the 1st ED visit, in rates of returned ED visits within 7 days, and in rates of hospital admission within 7

days, respectively, with 0.05 type I error. We have assumed that hospitalization rates are 35% and 50%, the 7-day returned ED rates are 30% and 15%, and 7-day hospitalization rates are 20% and 5%, in the patient-specific and weight-based analgesic protocols, respectively. The assumptions on the hospitalization rates and the return ED visit rates are based on the observations in the R34 study.

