14. ADVERSE AND SERIOUS ADVERSE EVENTS (TABLES)

14.1. Adverse Events

	Treatment A N=	Treatment B N=	Total N=	P-value
Nausea				
Vomiting				
Pruritis				
SPO₂ < 95% requiring supplemental oxygen via nasal cannula due to opioid therapy				
Moderate to Severe Sedation (Sedation Score of > 3)				
Drowsiness				
Respiratory Depression not requiring intubation				
Low Blood Pressure (SBP < 90mmHg and/or DBP < 50 mmHg)				

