14.2. Serious Adverse Events

	Treatment A N=	Treatment B N=	Total N=	P-value
Respiratory depression requiring naloxone administration given within the 2 hours of last administration of pain protocol drug Mild Moderate Severe Total				
Any event resulting in death Mild Moderate Severe Total				
Any event that is considered a life-threatening complication Mild Moderate Severe Total				
Any event requiring admission to the Intensive Care Unit (ICU) Mild Moderate Severe Total				
Any event requiring intubation Mild Moderate Severe Total				

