17. STUDY ENDPOINTS (TABLE)

17.1. Endpoints

	Treatment A N=	Treatment B N=	Estimate (95% CIs), SD	P-value
Change in Pain Score (Primary Endpoint)				
Length of Index ED Stay				
Hospitalization for Pain Control				
Return ED Visits				
Hospitalizations (if not admitted to hospital on Index ED visit)				
Re-hospitalizations (if admitted to hospital on Index ED visit, but discharged)				
Day Hospital Visits				
ED Revisits or Hospital Re-admissions or Day Hospital Visits Within 7 Days After the Index ED Visit (Binary Outcome with a Cutoff at Zero)				
Number of ED Revisits or Hospital Re-admissions or Day Hospital Visits After the Index ED visit				

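### The safety tables compare the arms by p-value alone, with no risk difference or confidence interval, so a non-significant row does not show how large an excess of harm the data still allow

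*SAP*

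**What the plan says.** Protocol 13.10 and SAP 4.3 use the same text. Side effects, AEs and SAEs are tabulated and described, and then: "Statistical comparisons of the randomized arms with respect to these events will use chi-square, Fisher exact or other appropriate two-sample methods". Both sections are headed exploratory. Both ask for the comparisons to be read against the efficacy results and with clinical judgment about how serious the events are.

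Protocol 13.6 sets the general criterion: "For all analyses, a two-sided p-value ≤ 0.05 will be considered statistically significant".

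The table shells show what will be reported:

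- SAP 14.1 (AEs), 14.2 (SAEs) and 15.1 (hospitalization): Treatment A, Treatment B, total, p-value.
- SAP 17.1 to 17.3 (endpoints, sensitivity analyses, subgroups): both arms, a column headed "Estimate (95% CIs), SD", and a p-value.

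SAP 7.6 adds bar charts for safety and no interval. Protocol 13.7 gives power for the primary outcome and for the secondary outcomes ("Power calculation for the secondary outcomes are performed for the target sample size of 230 at 0.05 level"). It gives no expected rate, relevant excess or power for any harm.

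**The concern.** The plan estimates benefit with an interval and compares harm by test only. Protocol 8.3 names dose as the main difference between the arms. In its Table 2 the repeat-dose entry for the patient-specific arm includes "No maximum dose set", while the weight-based arm limits how far a single dose may be raised. Protocol 12.4 lists sedation and respiratory depression among the known effects of the study drugs. Any pain benefit will therefore be weighed against opioid side effects, and SAP 4.3 itself asks for the two to be read together.

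That weighing needs the size of the excess and how uncertain it is. A p-value supplies neither. The trial was sized for a 14 mm pain difference, so for uncommon events a p-value above 0.05 says little. SAP 5 says the final report will be used for publication. A column of non-significant p-values could then be taken as equal safety, with nothing in the table to show what excess remains possible.

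**Working it through.** **Inputs from the documents.** Target 230 patients with an ED visit (Protocol 13.7); 1:1 allocation (Protocol 8.2), so n = 115 per arm; two-sided 0.05 (Protocol 13.6). The safety population is the modified ITT population with a completed AE form (SAP 7.1), so 115 per arm is the most to expect at this target.

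**Inputs assumed.** All safety event rates and illustrative counts. SAP 4.3 has no rule for choosing between the two tests. The main calculation uses Fisher when an expected count is below 5 or the smallest observed count is 5 or less, and Pearson chi-square otherwise. Results for each test used throughout are also shown.

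**Step 1: reproduce the plan's own figures.** The nearest stated figures are the 64%, 78% and 94% power for binary secondary outcomes in Protocol 13.7. With p̄ the mean of the two rates,

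power = Φ{ [ |p1 − p2| − 1.96·√(2p̄(1 − p̄)/n) ] / √[ (p1(1 − p1) + p2(1 − p2))/n ] }

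- 35% v 50%: (0.15 − 1.96 × 0.0652)/0.0644 = 0.345, power 63.5%
- 30% v 15%: (0.15 − 1.96 × 0.0551)/0.0542 = 0.776, power 78.1%
- 20% v 5%: (0.15 − 1.96 × 0.0436)/0.0425 = 1.519, power 93.6%

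All three agree with the protocol, so n = 115 and the test are read correctly.

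**Step 2: power for assumed harms.** Every pair of counts (x1, x2) from 0 to 115 is weighted by its two binomial probabilities, and the weights with p ≤ 0.05 are summed.

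| Assumed rates | Mixed rule | Fisher only | Chi-square only |
|---|---|---|---|
| 1% v 3% | 5% | 5% | 17% |
| 1% v 5% | 26% | 26% | 42% |
| 2% v 6% | 21% | 21% | 32% |
| 5% v 10% | 23% | 21% | 31% |
| 10% v 20% | 57% | 50% | 57% |
| 15% v 25% | 48% | 42% | 48% |
| 5% v 15% | 71% | 65% | 75% |
| 25% v 40% | 69% | 63% | 69% |

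The rate in the other arm needed for 80% power (normal approximation / exact Fisher) is 9.0% / 9.5% from 1%, 16.4% / 17.1% from 5%, 23.8% / 24.5% from 10%, and 47.9% / 48.8% from 30%. By subtraction, the detectable excess is about 8 points from a 1% base and about 11 to 19 points from bases of 5% to 30%.

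**Step 3: what an interval would add.** The Newcombe interval combines the Wilson limits (l, u) of each arm, where d is the difference in proportions:

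lower = d − √[(p1 − l1)² + (u2 − p2)²]; upper = d + √[(u1 − p1)² + (p2 − l2)²]

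For 5/115 v 1/115: p1 = 0.0435 (0.0187, 0.0978), p2 = 0.0087 (0.0015, 0.0476), d = 0.0348.

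- lower = 0.0348 − √(0.0248² + 0.0389²) = −0.011
- upper = 0.0348 + √(0.0543² + 0.0072²) = +0.090

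| Illustrative counts | Difference (points) | Newcombe 95% CI (points) | Fisher p |
|---|---|---|---|
| 5 v 1 | +3.5 | −1.1 to +9.0 | 0.21 |
| 12 v 6 | +5.2 | −2.0 to +12.7 | 0.22 |
| 35 v 23 | +10.4 | −0.8 to +21.4 | 0.094 |
| 5 v 0 | +4.3 | +0.3 to +9.8 | 0.060 |

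Each row is non-significant by Fisher, yet each is compatible with an excess of 9 points or more. With no events in one arm, the upper limit for that arm's rate is 1 − 0.025^(1/115) = 3.2%.

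**The case against.** **No wrong inference is planned.** A reader might infer that the trial intends to conclude there is no excess harm when p exceeds 0.05. The documents do not say so. The section is exploratory, the events are first described, and clinical judgment is required. Protocol 13.6 promises actual p-values and a cautious reading of secondary analyses. The phrase about other appropriate methods does not forbid an interval. All of this stands. It leaves a reporting gap: clinical judgment about seriousness does not supply the precision of a comparison, and the shells have no column for it.

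**The sample is not blind to harm.** A reader might also infer that the trial would miss most relevant opioid harms, or that non-significance is the expected result whenever a relevant excess exists. The documents give no harm rates and no relevant excess, so neither statement can be established. In three of the eight scenarios above the difference is detected more often than missed, and the plan's own 5% v 20% contrast has 94% power. This stands. Low power is shown for smaller excesses under the assumed rates, and not in general.

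**Other safety information is planned.** By-arm counts allow a reader to derive an interval. Sedation, oxygen saturation, respiration and blood pressure are shown every 30 minutes (SAP 7.4, table 16.1), cumulative opioid dose is summarised (SAP 7.5), and the DSMB reviews safety. This is true and widens the picture. The arm counts behind a binary endpoint would also allow an interval to be derived, yet table 17.1 plans to print one.

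**The dosing contrast is limited.** Table 2 restricts the size of a weight-based repeat dose but states no limit on the number of repeats. The contrast concerns dose size, and cumulative dose is not shown to be capped.

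**Conclusion.** The point holds as a gap in how safety is reported. Tests are the only between-arm method named for AEs and SAEs, tables 14.1, 14.2 and 15.1 give a p-value and no estimate or interval, and the endpoint tables give both. That part rests on the documents alone and needs no assumed rate.

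The size of the consequence does depend on assumption. At about 115 per arm, power is about 5% for 1% v 3%, 23% for 5% v 10% and 57% for 10% v 20%, rising to about 70% for 5% v 15% or 25% v 40%. A non-significant row can leave an excess of roughly 9 to 21 points open in the illustrative counts. If fewer AE forms are completed the intervals widen; if the sample is re-estimated upward they narrow.

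The documents do not support saying that a false claim of equal safety is planned, or that most relevant harms would be missed.

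**What to change.** 1. In SAP 4.3, name the risk difference (patient-specific minus weight-based) with a 95% confidence interval as the main between-arm safety summary. Specify a Newcombe or score interval, with an exact interval for sparse events, and say when each applies.
2. In tables 14.1, 14.2 and 15.1, add an estimate and 95% CI column, as in table 17.1. Keep the p-values as a secondary column.
3. State in SAP 4.3 that p > 0.05 will not be reported as absence of excess harm.

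A row for patients with any SAE is optional. A rule judging safety by the upper confidence limit is not recommended, because the documents define no acceptable excess to judge it against.

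The cost is a few sentences and one column per table, with no new data, patients or visits. Intervals for rare events will be wide and the safety statement less reassuring. For sparse counts the interval and the Fisher test may disagree: 5 v 0 gives +0.3 to +9.8 points by Newcombe beside p = 0.060. The SAP should say that the interval is then the main summary and that both are shown.

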5. OVERVIEW OF REPORT

This final report will be prepared by the Data Coordinating Center (DCC) and be used for the publication of study results.

The final report will summarize data and provide results of endpoints by treatment arm. All the calculations for the interim analyses will also be incorporated into the final analysis. These results will be intended for use by the Sponsor and other parties involved in the conduct of the study at the discretion of the Sponsor.

5.1. Purpose of Report

The primary purpose of the final report is to summarize selected baseline characteristics, adverse events, laboratory assessments, other safety measures, and results of study endpoints based on the final data. The final report will be based on modified intent-to-treat population only, and will include screening and baseline information on such subjects.

5.2. Report Production

SAS version 9.4 or later will be used to perform the analyses and create the graphics and tables for the report.

5.3. Abbreviated Report Outline

This report contains the following sections and chapters:

- Introduction
- Main Material
 - Patient Accountability
 - Baseline Characteristics
 - Assessments at the ED Visit
 - Adverse and Serious Adverse Events
 - Study Endpoints
- Supporting Material

This section will provide the same content as in the Main Materials, but in a tabular format with more numeric details.

5.4. Source of Data Included in Report

Study data will be collected through a customized web-based electronic data capture (EDC) system. The system that will be used is the Merge Healthcare's eClinical OS (eCOS), which has features that enable 21 CFR Part 11 compliance. eCOS is a flexible system for capturing, managing and reporting clinical research data in Phase I–IV studies. Randomization activities will also be conducted within the eCOS system at the DCRI.

6. REPORT STRUCTURE

6.1. Treatment Labels

Tables and figures will be grouped by treatment arms and total.

6.2. P-values

Except for the primary, secondary endpoints and safety outcomes for which we pre-specified methods to use in section 4, *P*-values, where applicable, for continuous or ordered categorical data are computed using the nonparametric Kruskal-Wallis test. This test is appropriate for data with non-normal distributions and has power near that of the Student's *t*-test when the data are normal. Pearson's chi-square or Fisher exact is used for dichotomous (e.g., gender) and unordered (e.g., race) categorical data. The log-rank test is used to obtain *p*-values for time-to-event endpoints. Cox modeling will be used for time-to-event outcomes if there are covariates, such as the initial pain score at ED arrival, biological variables of SCD genotype, age and gender.

6.3. Graphical Conventions

6.3.1. Bar Charts

Bar charts indicate for categorical data the number or percent of subjects by category. They are used to display a single categorical variable with mutually exclusive categories. Bar charts of related dichotomous variables are sometimes grouped together to form a multiple bar chart. A more detailed bar chart is used to display categorical data which has additional ordered subdivisions, as in the display of lab tests.

6.3.2. Box Plots

Boxplots indicate the distribution of continuous data based on percentiles (for example, the display for age and change from baseline). The top and bottom edges of the box represent the 25th and 75th percentiles of the data. The 5th and 95th percentiles are represented by the "whiskers" extending from the top and bottom of the box. The plotting symbol inside the box represents the median of the data.

Change from baseline. For variables which are measured at several fixed time points, change from baseline is usually provided for the observed data. For continuous variables, change can be given either in the original units or as percent change. For dichotomous variables, change from baseline can be indicated by displaying follow-up data separately for each baseline group.

6.3.3. Scatter Plots

For correlations of two continuous variables, scatter plots are used.

6.3.4. Annotations

Figures indicate the number of subjects used for the analysis, under the corresponding portion of the plot. *P*-values corresponding to the comparisons of the treatment groups are included, where applicable. Figures are also annotated with the data source.

7. NOTES ON ANALYSES

This section of the report *Introduction* contains additional details about analysis conventions and the contents of specific chapters.

7.1. General Conventions

The study population: The ITT population will consist of all patients randomized. The modified ITT population will consist of randomized adult SCD patients with an ED visit due to VOE. Summary of baseline characteristics and analysis of the primary endpoint will be done using the modified ITT population. The safety population will consist of all patients in the modified ITT population for whom the AE CRF is completed. Summaries of AE and SAE will be done using the safety population.

Treatment A and B will be replaced with actual treatment names after the database lock and study's unblinding. **Baseline records** are defined as those before the time of placement in treatment area of ED. **Denominators** will be the number of non-missing values of the variable in the analysis.

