9. STUDY ENROLLMENT AND COMPLETION AT ED VISIT

When the randomized patient has an ED visit for VOE, this patient is enrolled in the study population. The provider (un-blinded) in the ED will access the patient’s randomized analgesic protocol from the EMR for treatment. The patient will only be told what drugs and doses they will receive, but will not be told which analgesic protocol (weight-based or patient-specific) to which they have been randomized, thus the patient is blinded to the randomized arm. Research assistants (RAs), who are also blinded to study arm, will

interview the patient during an ED visit to obtain pain score data for the primary outcome. Only one ED visit per patient is recorded for the primary and secondary outcomes. The study is complete as soon as one post-randomization ED visit is recorded. The patient's randomized analgesic protocol will be removed from the EMR after the study ED visit is recorded. In the event where the ED visit is missed due to no availability of a RA (e.g., in the middle of the night), the next ED visit will be recorded. The RA will periodically review the EMR to obtain information on the missed ED visits for tracking purposes. During the ED visit, the maximum amount of time for study participation is six hours, which begins at placement in an ED treatment area. A brief interview will be conducted every 30 minutes until 1) discharge home, 2) admission to the hospital or assigned to observation status for continued pain management, or 3) after six hours of treatment (maximum data collection period), whichever comes first. Each patient will be allowed to contribute only one ED visit to the study data.

10. FOLLOW-UP DATA COLLECTION.

After the completion of the patient's recorded ED visit, the RA will periodically review the EMR to obtain the number of ED visits and number of hospitalizations within 7 days of the recorded ED visit for collection of secondary outcomes.

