12.5 Collection and Reporting of Adverse Events

An Adverse Event (AE) is any untoward medical occurrence associated with the use of a drug in humans, whether or not it is considered drug related. Only protocol- specific expected AEs occurring during the enrollment ED visit will be collected and reported on the AE eCRF.

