12.6 Collection and Reporting of Serious Adverse Events

An adverse event is considered a serious adverse event (SAE) if, in the view of the investigator or sponsor, results in any of the following: death, is life threatening, requires inpatient hospitalization or prolongation of existing hospitalization,* is a persistent or significant incapacity or substantial disruption of the ability to conduct normal life functions, a congenital anomaly/birth defect, or an important medical event. Only protocol-specific SAEs will be collected and reported on the SAE eCRF. Specific timing on collection and reporting of SAEs is specified below.

*For this protocol, if the study ED visit resulted in a hospitalization for pain control, this hospitalization will be considered the *index* hospitalization and will not be considered an SAE. Hospitalizations for VOE treatment within 7 days post the ED visits will also not be considered SAEs.

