 - ii. The patient is admitted to the hospital
 - iii. The patient is assigned to observation status for continued pain management
 - iv. The patient has received 6 hours of treatment

The best approach to missing data is to obtain complete data collection. Age, gender, and SCD type should be available for all patients. SCD type should be one of: Hgb SS, SC, or SB+, SB0 thalassemia. .

The trial will be closely monitored for missing time of bed placement or missing discharge, or 6 hours, pain scores. The first occurrence of missingness within a center will require explanation from the center and a plan to avoid missing data in subsequent patients.

For patients with dosing deviations, we plan to include them in the primary intent-to-treat analysis and collect all study measurements as planned.

Subgroup Analysis of the Primary Endpoint

We will examine whether the finding for the primary endpoint is similar for all patients, or whether it varies according to the following pre-specified subgroups. These will be assessed via interaction terms between treatment and subgroup categories tested at nominal 0.10 level.

- 1) Clinical site
- 2) Gender
- 3) Age (< 30, \geq 30 years old)
- 4) Genotypes (Hgb SS + SB0 and SC + SB+)
- 5) Route (IV or SC) - this will not be carried out if 90% or more subjects receive the IV route.
- 6) Use (yes/no) of NSAIDS
- 7) Drug administered
- 8) Number of repeated doses

9) Total administered milligrams of drug

These analyses will utilize the regression models with main effects and interactions between the randomized groups and pre-specified subgroup variables.

Details of presentation of results are illustrated in section 7.

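### SAE summaries are restricted to patients with a completed AE form, although SAEs are recorded on a separate form over a longer window (low severity)

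*SAP*

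**What the plan says.** SAP 7.1 sets the safety population: "The safety population will consist of all patients in the modified ITT population for whom the AE CRF is completed". The next sentence applies it to both kinds of event: "Summaries of AE and SAE will be done using the safety population". The same section says that denominators "will be the number of non-missing values of the variable in the analysis".

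The protocol keeps the two kinds of event on different forms. Section 12.5 says that only protocol-specific "expected AEs occurring during the enrollment ED visit will be collected and reported on the AE eCRF". Section 12.6 says that only protocol-specific "SAEs will be collected and reported on the SAE eCRF", and 12.6.1 runs SAE collection from the first protocol drug through 7 days after the visit. The schedules (Protocol Appendix A, SAP 3.3) mark AEs at the ED visit, and SAEs at both the ED visit and Day 7.

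SAP 5.1, which lists adverse events among the contents of the final report, says: "The final report will be based on modified intent-to-treat population only, and will include screening and baseline information on such subjects".

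On respiratory depression, the AE item in Protocol 12.5.1 excludes cases that need either intubation or naloxone. The matching item in SAP 7.6 and in the SAP 14.1 table shell excludes only intubation. SAP 14.2 lists naloxone-treated respiratory depression, within a time limit after the last dose, as an SAE.

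**The concern.** Whether a patient counts in the SAE table should depend on being in the analysed population, not on whether a different form with a shorter window was filled in. As SAP 7.1 stands, the AE form decides entry to both tables.

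The stake is the published SAE comparison. The repeat-dose rules differ between the arms (Protocol Table 2), so readers will weigh serious opioid harms against any gain in pain relief. The protocol-specific SAE list is narrow, and VOE hospitalizations are excluded from it (Protocol 12.6). Counts may therefore be small, and one lost patient could be visible.

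The naloxone wording raises a smaller issue of the same kind: one event could be classified differently depending on which document the programmer follows.

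**Working it through.** No figure in the plan is in dispute, so there is none to reproduce. The check is a comparison of text, followed by an illustration.

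**1. Forms and windows**

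| | AE | SAE |
|---|---|---|
| Form | AE eCRF (Protocol 12.5) | SAE eCRF (Protocol 12.6) |
| Window | Study ED visit | First protocol drug through 7 days after the visit (12.6.1) |
| Scheduled | ED visit | ED visit and Day 7 (Appendix A, SAP 3.3) |
| Condition for entering the table | Completed AE form (SAP 7.1) | Completed **AE** form (SAP 7.1) |

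The last cell is the problem. No other section of the SAP puts back a patient who has an SAE form but no AE form.

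**2. SAP 5.1 against SAP 7.1.** The safety population is a subset of the modified-ITT population. The two sections give the same N only if every modified-ITT patient has a completed AE form. Neither document says whether the form is completed for a patient who has no AE. The denominator rule does not say how it treats a patient without the form.

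**3. Illustration of size.** The planned modified-ITT size is 230 (Protocol 13.12). Let m be the share of patients without a completed AE form and k the number of patients with an SAE. Both are assumed, because the documents give neither. Missing forms are taken as unrelated to SAEs.

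- Patients leaving the SAE table = 230 × m
- Chance that at least one SAE patient is lost = 1 − (1 − m)^k

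| m | Patients leaving | N left | k = 1 | k = 2 | k = 3 |
|---|---|---|---|---|---|
| 0 | 0 | 230 | 0 | 0 | 0 |
| 2% | 4.6 | 225.4 | 2.0% | 4.0% | 5.9% |
| 5% | 11.5 | 218.5 | 5.0% | 9.8% | 14.3% |
| 10% | 23 | 207 | 10.0% | 19.0% | 27.1% |

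With 1:1 allocation an arm has about 230 / 2 = 115 patients, so one SAE patient is 1 / 115 = 0.9 percentage points. If missing forms were more common among patients with an SAE, the chances would be higher than shown. The missing-data rates in Protocol 13.7 concern the pain-score change and say nothing about AE forms.

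**4. Respiratory-depression items.** Take a case in the ED that is given naloxone inside the SAE item's time limit and is not intubated. Under Protocol 12.5.1 it is not an AE item, and under 12.6.1 it is an SAE. Under the SAP wording it meets both the 14.1 row and the 14.2 row. The SAP does not say whether rows may overlap.

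**The case against.** The strongest reply is that nothing may be lost. AE assessment is scheduled at every study ED visit, in the same table that schedules SAEs. A visit without a research assistant is not used: "In the event where the ED visit is missed due to no availability of a RA", the next one is recorded instead. Monitoring is every 30 minutes (Protocol Table 2). An SAE that arises after the visit comes when the AE window has already closed, so it is not an evident cause of a missing AE form. All of this stands. It makes near-complete forms likely, but the documents do not state completeness. If completion is universal, the condition does no work and can go; if it is not, the condition can remove SAE patients.

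A reader might infer that SAP 5.1 and 7.1 contradict each other. They do not. The safety set lies inside the modified-ITT population, and 5.1 can be read as keeping randomized patients without an ED visit out of the report. The two sections are unreconciled, no more.

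A reader might also infer that the AE form is filled in only when an AE occurs, so that the SAE denominator shrinks to patients with AEs. The documents do not say this, and the schedules point the other way.

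On naloxone, the SAP item may be only a shortened label. SAP 7.6 presents its list as the protocol's own items, and sites record events under the protocol. The AE and SAE shells are separate, with no combined total to inflate. That reduces the point to a request for consistent wording.

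**Conclusion.** The point holds at low severity. SAP 7.1 contains a stated rule that, read literally, drops a patient with a recorded SAE from the SAE table for want of a different form, and nothing else in the SAP overrides it. The size is unknown and is zero if every modified-ITT patient has a completed AE form. The range of 0 to 23 patients, and the chance of up to 19% of losing at least one of two SAE patients, rest on an assumed 0 to 10% of missing forms and on independence from SAEs. They are not evidence that any loss will occur.

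The documents do not support a claim that serious harms will be under-reported. Safety comparisons are exploratory (Protocol 13.10, SAP 4.3). SAEs are entered within 24 hours and passed on to NHLBI and the DSMB whatever the AE form status (Protocol 12.6.1). The primary and secondary endpoints are unaffected. The naloxone omission is a wording inconsistency, not proof of double counting.

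**What to change.** 1. In SAP 7.1, summarise SAEs on the whole modified-ITT population, the one named there for the primary endpoint, regardless of AE form completion. Use its full number per arm as the SAE denominator. This includes patients whose pain score is missing and those with dosing deviations, in line with SAP 4.1: "For patients with dosing deviations, we plan to include them in the primary intent-to-treat analysis and collect all study measurements as planned". It also settles the mismatch with SAP 5.1.
2. If a condition on receipt of protocol drug is wanted, because Protocol 12.6.1 opens the SAE window at first administration, state that condition explicitly instead of using form completion.
3. In the AE table (SAP 14.1), show by arm the number with a completed AE form and the number missing, and say how the non-missing denominator rule applies. State also that a patient with no SAE form counts as having no SAE, since a full SAE denominator implies this convention.
4. Reconcile the respiratory-depression AE item in SAP 7.6 and 14.1 with Protocol 12.5.1. A naloxone-treated case should not appear in both the AE row and the SAE row in 14.2 unless the SAP says that rows may overlap.

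The cost is wording in SAP 7.1 and 7.6 and two table shells. No new data are needed, and no clinical definition, time window or treatment rule is proposed.
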